### **6.6.2 Secondary Efficacy Assessments**

Secondary endpoints will include assessment of renal function including estimated GFR and rate of change in GFR, the need for and time to initiation of dialysis, the overall level of alloantibody as indicated by PRA and the incidence of infectious complications. GFR will be calculated based upon serum creatinine using the Diet in Renal Disease (study) formula as suggested by Levey et al. Subjects already requiring initiation of dialysis at

the time of enrollment will be excluded from the need for and time to initiation of dialysis analysis.

$$\text{GFR} = 170 \times (\text{SCr}/0.95)^{(-0.999)} \times (\text{Age})^{(-0.176)} \times (0.762 \text{ if the patient is female}) \times (1.180 \text{ if the patient is black}) \times (\text{BUN})^{(-0.170)} \times (\text{Alb})^{(0.318)}$$

GFR-glomerular filtration rate (ml/min), SCr-serum creatinine (mg/dL), Age in years, BUN- blood urea nitrogen (mg/dL), Alb-serum albumin (g/dL)

Laboratory efficacy parameters will be evaluated utilizing the main laboratory results

## 7 ADVERSE EVENT REPORTING

### 7.1 Adverse Events

An *Adverse Event (AE)* is defined as any new untoward medical occurrence or worsening of a pre-existing medical condition in a patient or clinical investigation subject administered an investigational (medicinal) product and that does not necessarily have a causal relationship with this treatment. An AE can therefore be any unfavorable and unintended sign (including an abnormal laboratory finding, for example), symptom, or disease temporally associated with the use of investigational product, whether or not considered related to the investigational product.

#### 7.1.1 Serious Adverse Events

A *Serious Adverse Event (SAE)* is any untoward medical occurrence that at any dose:

- results in death
- is life-threatening (defined as an event in which the subject was at risk of death at the time of the event; it does not refer to an event which hypothetically might have caused death if it were more severe)
- requires inpatient hospitalization or causes prolongation of existing hospitalization (see note below for exceptions)
- results in persistent or significant disability/incapacity
- is a congenital anomaly/birth defect
- is an important medical event, defined as a medical event that may not be immediately life-threatening or result in death or hospitalization but, based on appropriate medical and scientific judgment, may jeopardize the subject or may require intervention (eg, medical, surgical) to prevent one of the other serious

outcomes listed above. Examples of such events include but are not limited to intensive treatment in an emergency department or at home for allergic bronchospasm; blood dyscrasias or convulsions that do not result in hospitalization.

All pregnancies, regardless of outcome, must be reported to BMS, **including pregnancies that occur in the female partner of a male study subject. All pregnancies must be followed to outcome.** See Section 7.6 for instructions on reporting pregnancies.

Although overdose and cancer are not always serious by regulatory definition, these events should also be reported to BMS.

**NOTE:** The following hospitalizations are not considered SAEs in BMS clinical studies:

- a visit to the emergency room or other hospital department lasting less than 24 hours that does not result in admission (unless considered an “important medical event” or a life-threatening event)
- elective surgery planned before signing consent
- admissions as per protocol for a planned medical/surgical procedure
- routine health assessment requiring admission for baseline/trending of health status (eg, routine colonoscopy)
- medical/surgical admission for purpose other than remedying ill health state that was planned before study entry. Appropriate documentation is required in these cases.
- admission encountered for another life circumstance that carries no bearing on health status and requires no medical/surgical intervention (eg, lack of housing, economic inadequacy, caregiver respite, family circumstances, administrative).

### **7.1.2 Nonserious Adverse Events**

Nonserious adverse events are all adverse events that are not classified as SAEs.

## **7.2 Assignment of Adverse Event Intensity and Relationship to Investigational Product**

All adverse events, including those that are serious, will be graded by the physician investigator as follows:

- Mild (Grade 1): awareness of event but easily tolerated

- Moderate (Grade 2): discomfort enough to cause some interference with usual activity
- Severe (Grade 3): inability to carry out usual activity
- Very Severe (Grade 4): debilitating; significantly incapacitates subject despite symptomatic therapy.

The following categories and definitions of causal relationship to investigational product as determined by a physician should be used:

- **Related:** There is a reasonable causal relationship to investigational product administration and the adverse event.
- **Not Related:** There is not a reasonable causal relationship to investigational product administration and the adverse event.

The expression “reasonable causal relationship” is meant to convey in general that there are facts (eg, evidence such as de-challenge/re-challenge) or other arguments to suggest a positive causal relationship.

### 7.3 Collection and Reporting

Adverse events can be spontaneously reported or elicited during open-ended questioning, examination, or evaluation of a subject. To prevent reporting bias, subjects should not be questioned regarding the specific occurrence of one or more adverse events.

If known, the diagnosis of the underlying illness or disorder should be recorded, rather than its individual symptoms. The following information should be captured for all AEs: onset, duration, intensity, seriousness, relationship to investigational product, action taken, and treatment required. If treatment for the event was administered, it should be recorded in the medical record. The investigator must supply BMS and the IRB/IEC with any additional information requested, notably for reported deaths of subjects.

#### 7.3.1 Serious Adverse Events

Following the randomization of the subject, all SAEs must be collected, including those thought to be associated with protocol-specified procedures. Collection of all SAEs must continue for **8 weeks** after the last administration of the investigational product. If applicable, SAEs must be collected that relate to any later protocol-specified procedure (eg, a follow-up skin biopsy). The investigator should notify BMS of any SAE occurring

after this time period that is believed to be related to the investigational product or protocol-specified procedure.

All SAEs, whether considered related or unrelated to belatacept, must be reported to BMS (by the investigator or designee) within 24 hours of study personnel becoming aware of the event. If only limited information is initially available, follow-up reports are required. The original SAE form must be kept on file at the study site.

All SAEs should be faxed or emailed to BMS at:

**Global Pharmacovigilance & Epidemiology**  
**Bristol-Myers Squibb Company**  
**[contact]**  
**Email: [[contact]](mailto:[contact])**

For studies conducted under an **Investigator IND**, any event that is both serious and unexpected must be reported to the Food and Drug Administration (FDA) as soon as possible **and no later than 7 days** (for a death or life-threatening event) **or 15 days** (for all other SAEs) **after the investigator's or institution's initial receipt of the information**. BMS will be provided with a simultaneous copy of all adverse events filed with the FDA. SAEs should be reported on MedWatch Form 3500A, which can be accessed at: <http://www.accessdata.fda.gov/scripts/medwatch/>.

**Bristol-Myers Squibb Company**  
**[contact]**  
**Email: [[contact]](mailto:[contact])**

If the investigator believes that an SAE is not related to the investigational product but is potentially related to the conditions of the study (such as withdrawal of previous therapy, or a complication of a study procedure), the potential relationship should be specified in the narrative section of the SAE report.

If an ongoing SAE changes in its intensity or relationship to the investigational product, a follow-up SAE report should be sent immediately to BMS. As follow-up information becomes available it should be sent immediately using the same procedure used for transmitting the initial SAE report. All SAEs should be followed to resolution or stabilization.

### **7.3.2 Handling of Expedited Safety Reports**

In accordance with local regulations, BMS will notify investigators of all SAEs that are suspected (related to the investigational product) and unexpected (ie, not previously described in the Investigator Brochure). In the European Union, an event meeting these criteria is termed a Suspected Unexpected Serious Adverse Reaction (SUSAR). BMS will send investigators an expedited safety report (ESR) to notify them of such an event.

Other important findings that BMS may report as ESRs include increased frequency of a clinically significant expected SAE, an SAE considered associated with study procedures that could modify the conduct of the study, lack of efficacy that poses significant hazard to study subjects, clinically significant safety findings from a nonclinical (eg, animal) study, important safety recommendations from a study data monitoring committee, or the decision by BMS to end or temporarily halt a clinical study for safety reasons.

Upon receiving an ESR from BMS, the investigator must review and retain the ESR with the Investigator Brochure. Where required by local regulations or when there is a central IRB/IEC for the study, BMS will submit the ESR to the appropriate IRB/IEC. The investigator and IRB/IEC will determine if the informed consent requires revision. The investigator should also comply with the IRB/IEC procedures for reporting any other safety information.

In addition, BMS will report suspected serious adverse reactions (whether expected or unexpected) to the relevant health authorities in all concerned countries according to local regulations (either as expedited and/or in aggregate reports).

### **7.3.3 Nonserious Adverse Events**

The collection of nonserious adverse event (NSAE) information will begin at randomization. This NSAE information will also be collected from the start of a placebo lead-in period or other observational period intended to establish a baseline status for the subjects.

All identified NSAEs will be recorded and described in the medical record. If an ongoing NSAE worsens in its intensity, or if its relationship to the investigational product changes, a new NSAE entry for the event should be completed. NSAEs should be followed to resolution or stabilization, or reported as SAEs if they become serious. Follow-up is also required for NSAEs that cause interruption or discontinuation of investigational product, or those that are present at the end of study participation. Subjects with NSAEs at study completion should receive post-treatment follow-up as appropriate.

## **7.4 Laboratory Test Abnormalities**

All laboratory test values captured during treatment must be documented appropriately, including the following:

- any laboratory test result that is clinically significant or meets the definition of an SAE
- any laboratory abnormality that required the patient to have belatacept discontinued or interrupted
- any laboratory abnormality that required the patient to receive specific corrective therapy.

When reporting laboratory abnormalities, the clinical term rather than the laboratory term should be used by the reporter (eg, document “anemia,” not “low hemoglobin value”).

## **7.5 Overdose**

An overdose is defined as the accidental or intentional ingestion or infusion of any dose of a product that is considered both excessive and medically important. All occurrences of overdose must be reported as an SAE.

## 7.6 Pregnancy

Sexually active WOCBP must use an effective method of birth control during the course of the study, in such a manner that the risk of failure is minimized. (See Section 4.2.1 for the definition of WOCBP.) Before study enrollment, WOCBP must be advised of the importance of avoiding pregnancy during study participation and of the potential risk factors for an unintentional pregnancy.

### 7.6.1 Requirements for Pregnancy Testing

All WOCBP MUST have a negative pregnancy test within 72 hours before receiving belatacept. The minimum sensitivity of the pregnancy test must be 25 IU/L or equivalent units of HCG. If the pregnancy test is positive, the subject must not receive Belatacept and must not continue in the study.

In addition, all WOCBP must be instructed to contact the investigator and/or other study personnel immediately if they suspect they might be pregnant (eg, missed or late menstrual period) at any time during study participation.

### 7.6.2 Reporting of Pregnancy

If, following initiation of the investigational product, it is subsequently discovered that a study subject is pregnant or may have been pregnant at the time of investigational product exposure, including during 8 weeks after administration, the investigational product will be permanently discontinued in an appropriate manner (eg, dose tapering if necessary for subject safety). The investigator must immediately notify BMS of this event and record the pregnancy on the Pregnancy Surveillance Form (not on an SAE form). Initial information on a pregnancy must be reported immediately to BMS, and information on the outcome provided once it is available. Completed Pregnancy Surveillance Forms must be forwarded to BMS according to SAE reporting procedures.

**Note:** Any pregnancy that occurs in a female partner of a male study subject must be reported.

Protocol-required procedures for study discontinuation and follow-up must be performed for the subject unless contraindicated by pregnancy (eg, x-ray studies). Other appropriate

pregnancy follow-up procedures should be considered if indicated. Information regarding the course of the pregnancy, including perinatal and neonatal outcome, must be reported.

## **7.7 Other Safety Considerations**

Any significant worsening noted during interim or final physical examinations, electrocardiograms, x-rays, and any other potential safety assessments, whether or not these procedures are required by the protocol, should also be recorded in the medical record.

Subjects who prematurely withdraw or are terminated from study participation, for reasons other than withdrawal if consent, will be asked to continue in a reduced safety follow-up schedule. The study team will contact the patient every 3 months for the duration of the trial to assess patient survival, dialysis status, and serious adverse event occurrences.

## **7.8 Influenza Guidelines**

Per [current CDC influenza recommendations](http://www.cdc.gov/flu/professionals/vaccination/index.htm) for persons with immunosuppression, including those caused by medications, subjects should be counseled to obtain influenza vaccination in accordance with CDC guidelines

(<http://www.cdc.gov/flu/professionals/vaccination/index.htm>).

In addition, they will be advised to promptly contact a healthcare provider upon onset of any fevers or flu like symptoms in order to determine whether early or empirical antiviral therapy is indicated in accordance with CDC guidelines

(<http://www.cdc.gov/flu/professionals/antivirals/summary-clinicians.htm>).

# **8 STATISTICAL CONSIDERATIONS**

## **8.1 Sample Size Determination**

This is a single-center, randomized, controlled trial to evaluate the efficacy of belatacept to prevent the formation of donor-specific antibody in patients with a failing renal allograft thereby preventing sensitization and facilitating re-transplantation. Based on clinical and statistical judgment, it is anticipated that a sample size of 36 patients per group will provide valuable preliminary data to assess the impact of belatacept on this growing population of patients.

The sample size for each arm will be 36 patients (Phase I 18 patients in each arm, Phase II 18 patients in each arm, total for each phase 36 patients). From previous work it is assumed that the control arm will have about 60% of patients developing antibodies within a 3 year period. (unpublished results, analysis of patients at Emory Hospital) It is proposed that the group treated with belatacept will have a dramatic decrease in allo-antibody production. Assuming a rate of 20% in the treatment group, the power would be calculated at 90%.

## **8.2 Endpoint Definitions**

**Primary Endpoint:** The rate of donor-specific antibody formation 36 months following randomization.

**Secondary Endpoints:**

- Rate of change in GFR
- Time to dialysis measured from the time of randomization to initiation of dialysis
- Overall level of alloantibody as indicated by PRA.
- Incidence of infectious complications.

## **8.3 Analyses**

### **8.3.1 Demographics and Baseline Characteristics**

Demographic and baseline characteristics of subjects will be summarized descriptively by means and standard deviations for continuous variables and frequency distribution for categorical variables. Summaries will be performed based on all randomized subjects.

### **8.3.2 Safety Analyses**

All adverse events and serious adverse events will be summarized by treatment group. Serious adverse events will be collected and summarized following the subject's written consent to participate in the study. Non-serious adverse events will be collected and summarized beginning at the time of randomization. Laboratory abnormalities will be descriptively summarized.

### 8.3.3 Efficacy Analyses

There will be two main methods of analyzing the primary outcome at the study end. One will be a chi-squared test comparing the proportion of patients who developed donor specific antibodies in each study group. The second analysis will be a log-rank test comparing the Kaplan-Meier time to event curves between the two study groups. In both cases we will use a two-sided test with a significance level of 0.05.

The sample size for each arm will be 36 patients. This sample size calculation is based on several assumptions. We assume that the incidence of developing donor-specific antibody among the control group is 60% and among the belatacept-treated group it is 20% or less. We also assume an alpha level of 0.05 and corresponding  $Z\text{-alpha} = 1.96$  and a one-to-one ration of exposed to unexposed subjects. Calculations with these estimates yield a power of 90% to detect a three-fold difference in risk of developing donor specific antibodies between the control and belatacept-treated group.

In addition to the aforementioned assumptions, additional assumptions required for the log-rank test include no loss to follow-up in 36 months and that the distribution of the incidence of the primary endpoint follows an exponential distribution. Assuming an incidence of development of anti-donor antibody in the control group is 60% at 36 months then the hazard rate can be calculated as 0.02545. In the treatment arm, if the incidence of the primary endpoint is 30% then the hazard ratio becomes 0.0099 and if the incidence is 20% then the hazard rate is 0.00619.

Analysis of secondary endpoints will be performed at the end of the study period. Differences in the mean level of allo-antibody (ie PRA) by control and belatacept-treated groups will be compared using a t-test statistic. The rate of decline of GFR among the belatacept group will be compared to the rate of decline of the control group using a Rate Ratio and corresponding 95% Confidence Intervals using the Mantel-Haenszel chi-square test statistic for significance. The time from randomization to initiation of dialysis will be compared between groups using Kaplan-Meier analysis and the log-rank test for significance. The small subset of subjects already requiring dialysis at the time of enrollment will be excluded from this analysis. The incidence of overall infectious episodes will be compared among the belatacept vs. control group by calculating a Risk Ratio and corresponding 95% Confidence Intervals and using the Mantel-Haenszel chi-

square test statistic for significance. For all secondary endpoint analyses, two-tailed  $p < 0.05$  will be considered statistically significant.

Interim analyses will be performed at 18 months to compare the primary endpoint between the belatacept-treated and control groups, using the log-rank test for significance. A two-sided test with a more stringent significance level of 0.001 will be used to preserve the overall significance level of the trial.

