| Statistics: | 
There will be two main methods of analyzing the primary outcome at the end of the study. One will be a chi-squared test comparing the proportion of patients who developed donor-specific antibody in each study group. The second analysis will be a log-rank test comparing the survival curves (survival being defined as the time until development of donor specific antibody) between the two study groups. A separate set of similar analyses will evaluate both the need and time to initiating dialysis. Subjects requiring dialysis at the time of enrollment will be excluded from this analysis. In both calculations there are similar assumptions made; we will use a two-sided test with a significance level of 0.05 and the sample size for each arm will be 30 patients. Other measures that will be evaluated with standard statistical methods include the change in PRA, the level of allo-antibody intensity, GFR and change in GFR.
 |
|--------------------|---|

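### The primary outcome has two main tests, chi-squared and log-rank, each at two-sided 0.05, with no rule for which decides the trial or how a split result is read

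*Combined protocol and SAP*

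**What the plan says.** Section 8.3.3 opens with "There will be two main methods of analyzing the primary outcome at the study end". The first is described so: "One will be a chi-squared test comparing the proportion of patients who developed donor specific antibodies in each study group". The second is a log-rank comparison of Kaplan-Meier curves. On the level it says: "In both cases we will use a two-sided test with a significance level of 0.05". The Statistics row of the Synopsis repeats the pair ("There will be two main methods of analyzing the primary outcome at the end of the study") at the same level.

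Other parts of the plan point in different directions:

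- Section 8.2 defines the endpoint as "The rate of donor-specific antibody formation 36 months following randomization", and the 90% power in Section 8.3.3 is for a difference in risk. Both suggest the chi-squared test.
- The 18-month interim analysis in Section 8.3.3 uses the log-rank test only.

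The only alpha adjustment is for that interim look: "A two-sided test with a more stringent significance level of 0.001 will be used to preserve the overall significance level of the trial".

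**The concern.** Both tests are called main, both have the full 0.05, and neither is subordinate. The plan does not say whether success means either test, both tests or one named test. These rules have different false-positive rates. If the two p-values fall on opposite sides of 0.05, the plan has no answer, and the choice can be made with the results in view.

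The tests can part company for two reasons. The log-rank test uses the timing of DSA and the chi-squared test does not. DSA follow-up can also end early: under Section 7.7, subjects who leave for reasons other than withdrawn consent are contacted "every 3 months for the duration of the trial to assess patient survival, dialysis status, and serious adverse event occurrences", which does not include DSA. The log-rank test censors such subjects. The plan does not say how the chi-squared test counts them.

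**Working it through.** **Inputs from Section 8.3.3:** 36 per arm; DSA by 36 months 60% in control and 20% with belatacept; a 30% case also appears ("In the treatment arm, if the incidence of the primary endpoint is 30" per cent); exponential times; no loss; two-sided 0.05.

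**Assumptions, because the plan gives no figure:** loss of 15% or 30% by month 36, independent of DSA, with lost subjects counted as DSA-free in the chi-squared test.

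**1. The plan's own figures.** The hazard is −ln(1 − p)/36:

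- 60%: 0.9163/36 = 0.02545
- 30%: 0.3567/36 = 0.00991
- 20%: 0.2231/36 = 0.00620

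These match the plan to rounding.

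For chi-squared power at 60% versus 20%, the mean proportion is 0.4. The null SE is √(2 × 0.4 × 0.6/36) = 0.1155, and the alternative SE is √((0.24 + 0.16)/36) = 0.1054.

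- Uncorrected: (0.4 − 1.96 × 0.1155)/0.1054 = 1.65, power 95.0%.
- Continuity-corrected: (0.4 − 1/36 − 1.96 × 0.1155)/0.1054 = 1.38, power 91.7%.

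The stated 90% at 36 per arm is closer to the corrected test. However, the uncorrected formula needs 30 per arm for 90% power, which is the Synopsis figure. The plan therefore does not settle which chi-squared test is meant.

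For the log-rank test, expected events are 36 × (0.6 + 0.2) = 28.8 and the hazard ratio is 0.00620/0.02545 = 0.2435. By Schoenfeld's formula, 1.413 × √(28.8/4) − 1.96 = 1.83, power 96.6%.

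**2. False-positive rate by decision rule.** Two independent tests would give 1 − 0.95² = 9.75%. That is too high here, because both tests use the same data. I simulated both tests on the same trials (60,000 per scenario; Monte Carlo standard error about 0.1 points).

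| 36 per arm, null | Either test, uncorrected chi-squared | Either test, corrected chi-squared |
|---|---|---|
| 60%, no loss | 6.4% | 5.4% |
| 40%, no loss | 5.6% | 5.0% |
| 20%, no loss | 5.3% | not reported |
| 60%, 15–30% loss | 6.4–6.8% | not reported |

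At the 60% null with no loss, the log-rank test alone rejects in 5.2%, the uncorrected chi-squared in 4.9% and the corrected one in 2.6%. Requiring both log-rank and uncorrected chi-squared gives 3.7%.

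**3. How often the tests disagree (36 per arm).**

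| True rates | Loss | Uncorrected chi-squared | Corrected chi-squared |
|---|---|---|---|
| 60% vs 20% | none | 1.4% | 3.9% |
| 60% vs 20% | 30% | 4% | 7.7% |
| 60% vs 30% | none | 5% | 11.4% |
| 60% vs 30% | 30% | 10% | 16.0% |

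The corrected column is from 20,000 trials per scenario.

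**4. Visit schedule.** With DSA detected only at months 1, 2, 3, 6, 9, 12, 18, 24, 30 and 36, the either-test rates (uncorrected) are 6.2%, 5.9% and 5.2% at nulls of 60%, 40% and 20%. Disagreement at 60% versus 30% is 5.0% with no loss and 10.6% with 30% loss.

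**5. Interim look.** At the 60% null, the log-rank test with an 18-month look at 0.001 rejects in 5.2%, the same as the final log-rank alone. A look at 0.05 would give 8.0%. The 0.001 level does its job for the early look but leaves the second final test uncovered.

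**6. Phase I only (18 per arm, 60% null, no loss).** The either-test rate is 7.1%, but the uncorrected chi-squared alone already rejects in 6.0%. With correction, the either-test rate is 5.4%.

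**The case against.** The case against turns on size. At the planned effect with no loss the tests rarely disagree. Inflation arises only under an either-test rule, which the plan neither states nor excludes, and it almost disappears if the chi-squared test is continuity-corrected. The 10% disagreement figure needs a smaller effect than planned, 30% loss, and lost subjects counted as DSA-free. Section 8.1 describes the aim as preliminary data from one center. All of this stands and keeps the point moderate. The correction works both ways, however: it removes most of the inflation but raises disagreement.

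Section 6.1 brings forward the next scheduled assessments when a subject withdraws, so DSA status near exit may be known. Section 6.3 specifies intention to treat. Neither says how a subject without 36-month data is counted, and neither ranks the two tests.

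A preference for the log-rank test can also be disputed. The endpoint wording and the power statement lean towards chi-squared. Censoring may be informative or differ by arm: Section 6.5 has belatacept subjects on dialysis leave the study for persistent positive EBV titers. This is why the fix accepts either test. Handling of missing DSA data will need its own rule whichever test is chosen.

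**Conclusion.** The concern holds. The plan has two main tests of one outcome, each at full alpha, and no decision rule. The main harm is the open choice of deciding test after the data are seen; the extra alpha is secondary. At 36 per arm with no loss, an either-test rule would cost at most about 1.4 points (6.4% against 5%), and requiring both would cause no inflation. Disagreement is uncommon at the planned effect and more frequent at 60% versus 30%.

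The no-loss figures rest on the plan's own rates and exponential model. The loss figures rest on the assumed loss rates and counting rule. The plan should be corrected on this point, but the point does not undermine the design.

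**What to change.** In Section 8.3.3 and the Synopsis, name one test as the single decisive primary analysis at two-sided 0.05, and label the other supportive with no claim attached.

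- **If log-rank:** this is a reasonable choice, because it is already the interim test and it censors subjects whose DSA follow-up ends early. Report the Kaplan-Meier difference in 36-month DSA rates with a 95% confidence interval beside it, to match the endpoint in Section 8.2.
- **If chi-squared:** this resolves the point equally well, provided the plan also states whether it is continuity-corrected and how subjects without 36-month DSA data are counted.

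The cost is one sentence in each of the two places and the loss of a second chance at significance. The sample size does not change. Simulated power at 60% versus 20% with no loss is 95.2% for log-rank and 94.9% for uncorrected chi-squared at 36 per arm. At 18 per arm, log-rank is about 2 points lower (72.3% versus 74.3%), but there the uncorrected chi-squared exceeds its nominal level (6.0% at a 60% null).
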